The operation for the pharmacy administration and dispensing of methadone for OUD treatment will be based on the available treatment guidelines for pharmacy-based medication management and Medication-assisted treatment (MAT) for OUD, including SAMHSA's guidelines to the federal OTP regulations and the guideline for pharmacy-based supervision of methadone consumption from other countries (Adams et al., 2015; Hill, 2014; Ontario Pharmacists Association, 2017; SAMHSA, 2015a, 2015b; SAMHSA, 2018a;). An Operational Care Agreement (OCA) will be used to define the respective roles of the methadone medical provider (supervising care and writing prescriptions) and pharmacist and determine study procedures. The OTP will continue to follow routine care practices and procedures as usual during the study and provide counseling, medical supervision, and urine drug testing. The study pharmacist will administer and dispense methadone according to the OTP provider's prescription.

Participants will be assessed at baseline (following informed consent). Outcome assessments will be conducted at each monthly visit throughout the follow-up phase of the study. Assessments will focus mainly on the feasibility and acceptability of pharmacy-based methadone administration and dispensing in order to inform the development of a future multisite randomized clinical trial. **Primary outcome** will be medication adherence. Measures of adherence will include: (1) adherence to scheduled pharmacy visits for dose administration and take-home pickup and (2) success in methadone call-back (e.g., failed methadone dose call back as an indicator treatment non-adherence). **Secondary outcomes** will include recruitment rate, treatment retention, opioid and other substance use, participant treatment satisfaction, pharmacist and physician treatment satisfaction, and participant safety. Information generated from this pilot study will inform the development of a future randomized controlled trial, which will test the effect of pharmacy-OTP collaborative care model for the management of patients with OUD.

2. Objectives

The overarching goal is to explore the feasibility and acceptability of transferring methadone dose administration and take-home methadone dispensing for OUD treatment for stable patients from OTPs to pharmacies. We will achieve this goal by pursuing the following primary pilot study objectives.

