- a) Calculate the rate of recruitment, defined as the number of participants enrolled in the study out of the number of MMT patients who are potentially eligible and approached for participation. The average monthly rate of participants starting pharmacy-based methadone dispensing for OUD among enrolled participants will also be calculated. The number of potential participants pre-screened and the reasons for pre-screen failure and screen failure will also be evaluated.
- b) Calculate the adherence to methadone treatment defined as (1) the proportion of methadone take-home doses dispensed at the pharmacy out of the total number of take home doses prescribed and (2) the proportion of successful scheduled methadone dose call-back with no signs of methadone diversion.
- c) Examine retention in treatment, as determined by the proportion of participants who remain in treatment at the pharmacy during the 3-month follow-up phase.

- d) Examine the proportion of positive urine drug screens (UDS) over the study duration.
- e) Examine the number of days of self-reported substance use (alcohol intoxication, and other drugs) as collected on Timeline Followback (TLFB) over the study duration (Sobell, 1992; Sobell & Sobell, 2000).
- f) Determine indicators of participant satisfaction with treatment delivery measured using the Treatment Satisfaction Survey (adapted from Harland et al., 2005) obtained at each assessment; proportion of visits in which raters are satisfied (score of 4 on a Likert Scale of 1-5) or very satisfied (score of 5 on a Likert Scale of 1-5).
- g) Determine pharmacist and physician satisfaction with treatment delivery measured using the Treatment Satisfaction Survey at follow-up assessment, and a proportion of physician and pharmacist ratings of satisfied or very satisfied.
- h) Examine participant safety, as measured by: (1) Any fatal or non-fatal substance-related overdose measured by medical examiner record or self-report, respectively; and (2) Any substance-related emergency department (ED) visit or hospitalization, measured by self-report.

3. Background and rationale

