4.4. Assessments

Study assessments will focus on the feasibility (e.g., recruitment, implementation of the intervention), treatment adherences, and safety measures. A list of assessments by the study visit is summarized in **Table 1**. Assessments are categorized as either general and medical assessments, safety assessments, substance use assessments, or methadone treatment and satisfaction assessments. A detailed description of each assessment is provided following the study assessment timetable.

Table 1: Study Assessment Timetable

Study visit number	Visit 1	Visit 2*_	Visit 3	Visit 4	Visit 5	Early termination	
Visit location**	OTP/remote	Pharmacy	OTP, Pharmacy, remote	OTP, Pharmacy, remote	OTP, Pharmacy, remote	OTP, Pharmacy, remote	
Assessment/Activity	Screening/ Baseline	Methadone dosing and dispensing	1 Month After Visit 2	2 Months After Visit 2	3 Months After Visit 2		As needed
General and Medical Assessments							
Recruitment Log	x						
Prisoner Status Assessment	x		x	x	x		x
Informed Consent/HIPAA/ Medical Release Form	x						x
Master Enrollment Log	x						
Inclusion/Exclusion Checklist +	x						
Locator Form	x		x	x	x		x
Demographics	x						
Medical History	x						
Substance use history	x						
Charlson Comorbidity Index	x						
Concomitant Medications	x		x	x	x		x
Study Completion					x	x	
Protocol Deviations							x
Missed Visit							x
Safety Assessments							
Patient Health Questionnaire (PHQ-9)	x		x	x	x	x	
P4 suicide screener (P4 screener) (Follow-up assessment will be triggered by the PHQ-9 result) ++	x		see ++	see ++	see ++		x
Safety Event Response Checklist	x		x	x	x		x
Pregnancy and birth control assessment	x		x	x	x		x
Substance Use Assessments							
Urine Drug Screen (UDS) (the OTP records)	x		x	x	x		x
Timeline Followback (TLFB)	x		x	x	x	x	
Methadone Treatment and Satisfaction Assessments							
Methadone Call Back (once)			see +++	see +++	see +++		x+++

Study visit number	Visit 1	Visit 2*_	Visit 3	Visit 4	Visit 5	Early termination	
Visit location**	OTP/remote	Pharmacy	OTP, Pharmacy, remote	OTP, Pharmacy, remote	OTP, Pharmacy, remote	OTP, Pharmacy, remote	
Assessment/Activity	Screening/Baseline	Methadone dosing and dispensing	1 Month After Visit 2	2 Months After Visit 2	3 Months After Visit 2		As needed
(the OTP records)+++							
OTP's Psychosocial Counseling Attendance Form (the OTP records)	x		x	x	x	x	
Methadone Visit Checklist++++		x	x	x	x		x
End of Methadone Medication Form					x	x	
Treatment Satisfaction Survey	x		x	x	x	x	

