* Visit 2 refers to the pharmacy visit for the **first** methadone dose administration. The timing of the subsequent follow-up visits are anchored at visit 2.

** Remote pre-screening and screening, remote consenting (eConsent), and remote data collection (study assessments) by phone or the Duke-approved teleconferencing platform for research also will be used.

+ Inclusion/exclusion criteria: Medical record data at the OTP will be used to determine study eligibility status.

++ P4 Screener: Follow-up assessment for suicide risk by P4 Screener will be triggered by the PHQ-9 result. Endorsements of suicidality on the PHQ-9 (i.e., if the participant answers Q9 "Thoughts that you would be better off dead, or of hurting yourself in some way" as "Several days", "More than half the days" or "Nearly every day") will trigger the completion of the P4 Screener form. A positive finding will be reported promptly to Site PI for further medical evaluation and clinical decision.

+++ Methadone Call Back: At least one random methadone call-back visit will occur during the study period (i.e., after the first methadone dispensing at the pharmacy).

++++ Methadone Visit Checklist: Methadone for Opioid Use Disorder will be administered and dispensed by study pharmacist(s) at Visit 2 (after enrollment into the study) and subsequently according to the length of time prescribed by the OTP physician for a total of 3 months. This form will be completed by the study pharmacist at each pharmacy visit. The number of pharmacy visits will be based on each participant's methadone take-home doses and treatment schedule.

4.4.1. General and Medical Assessments (Note: The visit numbers used in this section follow the order indicated in the Study Assessment Timetable.)

Recruitment Log: Drawing on the information captured in the Master Enrollment Log, as well as by reviewing the signed consent forms, the Recruitment Log will collect data on the number of potential participants who have been pre-screened for participation in the study and the number of participants who signed the informed consent form. These data will be used monthly to calculate the recruitment rates during the month enrollment phase. Data from this log will be used to project the number of participants and inform the duration of enrollment (i.e., recruitment rate) for a future multi-site clinical trial.

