satisfaction with treatment will be recorded on the Treatment Satisfaction Survey (based on a 5-point Likert scale: 0 = very dissatisfied, to 5 = very satisfied) that is completed by study participants at each study visit (1-4), including the Early Termination Visit (if participant discontinues study participation early). Pharmacists and physicians will also be asked to complete the Treatment Satisfaction Survey once per month, beginning the month of the first participant, first visit (FPFV; Visit 1) at their paired site and ending the month of the last participant, last visit (LPLV) at their paired site.

End of Methadone Medication Form: This form tracks the participant's status with regard to the study intervention/medication. It will be completed at the pharmacy at the Early Termination Visit (if participant discontinues study participation early), or at the LAST visit at the pharmacy for methadone administration and dispensing, which will occur about 3 months after the first pharmacy visit. Remote/virtual interviews by phone or the Duke-approved teleconferencing platform for research may be used to collect study assessments for participants who discontinue study participation early and are unable to return for Early Termination Visit during the specified time period.

Methadone Treatment Education Feedback Questionnaire: We will collect the opinions of pharmacists and OTP physicians about the clarity and utility of the study training materials, as well as any lack of useful information from the training. The questionnaire will consist of specific questions on the training modules to be rated on a 5-point Likert Scale of satisfaction, and will be filled out at the end of the training phase and once all participants have completed the study. The results will be used to structure training materials for a subsequent clinical trial.

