13.2. Secondary Outcome Measures

- **Rate of recruitment of participants into trial:** The recruitment rate will be assessed on a monthly basis until the enrollment target is reached. The recruitment rate is operationalized as the total number of participants consented in one month. The per-month proportion of consented participants reaching the pharmacy follow-up phase will also be calculated, as well as the per-month proportion of pre-screened participants that were consented. These rates will be used to estimate the speed at which a future multi-site RCT could consent, enroll, and randomize participants.
- **Treatment retention in follow-up assessments:** Retention in follow-up assessments is defined as the proportion of study assessments completed (three follow-up assessments).
- **Opioid and other substance use:** The prevalence and frequency of opioid/heroin use and other substance use over the study duration will be examined.
- **Satisfaction of participants, physicians, and pharmacists with OUD care**

Satisfaction with treatment delivery by participants will be measured using the Treatment Satisfaction Survey (adapted from Harland et al., 2005) at each visit. The proportion of visits in which participants are satisfied (score of 4 on a Likert Scale of 1-5) or very satisfied (score of 5 on a Likert Scale of 1-5) will be calculated. Pharmacist and physician satisfaction with treatment delivery will be measured using the Treatment Satisfaction Survey on a monthly basis, and a proportion of physician and pharmacist monthly ratings of satisfied or very satisfied will be calculated.

- **Participant safety, as measured by:**

- a) Any fatal or non-fatal substance use-related overdose measured by self-report.
- b) Any substance use-related ED visit or hospitalization measured by self-report.

13.3. Statistical plan and data analysis.

This is a feasibility study, and as such there are no a priori hypotheses. The main objective is to understand the feasibility regarding the study design features and operational procedures in order to inform the design of a full scale clinical trial (e.g., whether participants can be recruited in a timely fashion, whether the collaboration between the OTP and pharmacist can ensure standard methadone treatment for Opioid Use Disorder).

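### The participant satisfaction proportion, as defined, counts a Visit 1 rating made before any pharmacy dosing, so one in four of a completer's ratings reflects OTP dispensing

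*Combined protocol and SAP*

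**What the plan says.** Section 13.2 (Secondary Outcome Measures) has participants complete the survey at each visit and reports "The proportion of visits in which participants are satisfied (score of 4 on a Likert Scale of 1-5) or very satisfied", the latter being a score of 5. Objective (f) in Section 2 has the same content, with the survey "obtained at each assessment; proportion of visits in which raters are satisfied". Neither sets any visit aside.

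The schedule is in Table 1 (Section 4.4). The row "Treatment Satisfaction Survey" is marked at Visit 1, at Visits 3, 4 and 5 (months 1, 2 and 3) and at Early Termination, and is blank at Visit 2. Section 4.4.4 also includes Visit 1: the survey is "completed by study participants at each study visit (1-4", plus Early Termination.

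Pharmacy dosing begins after that baseline rating. A Table 1 footnote states: "Methadone for Opioid Use Disorder will be administered and dispensed by study pharmacist(s) at Visit 2 (after enrollment into the study". The Abstract likewise moves dispensing from the OTP to the pharmacy only after the baseline assessment.

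Other text bears on the point less directly. The Abstract says: "Outcome assessments will be conducted at each monthly visit throughout the follow-up phase of the study". Section 13.3 says GEE models will be considered for outcomes repeated in the follow-up phase. Retention, in Section 13.2, is limited explicitly: "defined as the proportion of study assessments completed (three follow-up assessments".

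**The concern.** The Abstract gives as a study aim the satisfaction of patients and providers with pharmacy administration and dispensing of methadone. At Visit 1 the participant has not yet been dosed at the pharmacy, so that rating cannot describe it. Pooling it with the later ratings pulls the result toward satisfaction under OTP dispensing whenever the two differ, in a direction that cannot be known beforehand.

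There is a second loss. In a single-group study, the Visit 1 rating is the only scheduled one made under OTP dispensing. Kept apart, it allows a within-person comparison; absorbed into the pooled proportion, it does not.

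Because the text gives no instruction to leave Visit 1 out, two analysts could also report different figures from the same data, and the choice could be made after the ratings are seen.

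**Working it through.** The plan states no expected satisfaction rate, so there is no figure of its own to reproduce. The check counts ratings and then works out the effect of pooling.

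**Ratings per completer (Table 1).** Visit 1: 1; Visit 2: 0; Visits 3, 4 and 5: 1 each. Total 4, of which 1 precedes the first pharmacy dose. Share = 1/4 = 25%. With the maximum of 20 participants (Section 4.1), all completing: 20 × 4 = 80 ratings, 20 before pharmacy dosing and 60 after.

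**Effect on the reported figure.** Let b be the proportion satisfied at Visit 1 and f the proportion satisfied over follow-up. With complete data:

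- reported = 0.25 × b + 0.75 × f
- error = reported − f = 0.25 × (b − f)

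All values of b and f below are assumptions.

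| b | f | Reported | Error (points) |
|---|---|---|---|
| equal to f | any | f | 0 |
| 90% | 80% | 82.5% | +2.5 |
| 90% | 70% | 75.0% | +5.0 |
| 90% | 60% | 67.5% | +7.5 |
| 50% | 90% | 80.0% | −10.0 |

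If both rates may lie anywhere from 50% to 100%, the error runs from 0.25 × (50 − 100) = −12.5 to 0.25 × (100 − 50) = +12.5 points.

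**Early stopping raises the baseline share.** Suppose 4 of 20 stop after month 1 (assumption).

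- No Early Termination rating: 16 × 4 + 4 × 2 = 72 ratings; share 20/72 = 27.8%; error at 90%/60% = 0.278 × 30 = 8.3 points.
- With an Early Termination rating: 16 × 4 + 4 × 3 = 76 ratings; share 20/76 = 26.3%; error 7.9 points.

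**No analysis set is named.** Baseline assessments follow consent and help decide eligibility (Section 4.2), and Section 17 provides for screen failures after consent. Section 13.2 does not say whose ratings count, so someone who never reaches the pharmacy could contribute a Visit 1 rating alone.

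**Precision if Visit 1 is left out.** For m ratings per person, 20 people, an assumed 80% satisfied and within-person correlation ρ:

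SE = √[0.8 × 0.2 / 20 × (1 + (m − 1)ρ) / m]

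| ρ | m = 4 | m = 3 |
|---|---|---|
| 0.5 | 7.1 points | 7.3 points |
| 0 | 4.5 points | 5.2 points |

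**The case against.** The best defence is that the plan, read as a whole, treats Visit 1 as baseline. The Abstract assigns outcome assessment to the follow-up phase, in the same paragraph that lists satisfaction as a secondary outcome. Section 4.2 says baseline data serve mainly to settle eligibility, and the GEE sentence refers to follow-up. A sensible analyst might well exclude Visit 1 unprompted, and the schedule records which visit each rating belongs to, so the split could still be made later. This shows that the intention may be sound, but general statements do not override a specific definition that counts visits without exception. The contrast with retention supports the literal reading only modestly, because that outcome is about follow-up assessments by its nature.

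A second objection is that the ratings do not divide cleanly into OTP and pharmacy. The survey asks about treatment quality overall, and counselling, medical oversight and urine testing stay at the OTP throughout. That stands: ratings after Visit 2 are not a pure measure of pharmacy dispensing, and what each rating refers to is inferred from timing. It does not make a rating given before any pharmacy dose informative about pharmacy dosing.

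Third, the size rests on assumed rates. The direction is unknown, the largest errors need gaps of 30 to 40 points, and the 2.5- and 5-point errors are smaller than a standard error of about 7 points (correlation 0.5). The outcome is secondary and descriptive, with no threshold attached. All of this stands and limits the weight of the point. It does not justify keeping a definition that blurs a stated aim when the correction is nearly free.

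**Conclusion.** The concern holds. Under the definition in Sections 2(f) and 13.2 and the schedule in Table 1, 25% of completers' ratings (20 of 80 if all 20 complete) precede pharmacy dosing. The reported proportion is shifted by 0.25 × (baseline − follow-up): nothing if the rates are equal, +7.5 points at an assumed 90%/60%, −10 points at an assumed 50%/90%. Early stopping raises the baseline share somewhat.

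The count of ratings follows from the documents; the point sizes depend on assumed rates. No test or sample size is affected. This should be corrected, because the figure reports on a stated aim.

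Three smaller inconsistencies should be reconciled at the same time; the main point depends on none of them:

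- **Scale.** Section 4.4.4 describes a "5-point Likert scale: 0 = very dissatisfied, to 5 = very satisfied", which spans six scores, while Sections 2(f) and 13.2 use 1 to 5. A score of 4 or 5 is the top two either way, so this alone probably changes little.
- **Visit numbers.** In Table 1's numbering, the 1-4 in Section 4.4.4 omits month 3 (Visit 5) and takes in Visit 2, where no survey is scheduled. On the baseline-plus-three numbering apparently used elsewhere in Sections 4.4.1, 4.4.2 and 15.2, it matches the four survey points. Visit 1 is included on either reading.
- **Clinician ratings.** Section 2(g) places them at follow-up; Section 4.4.4 starts them in the month of the first participant's Visit 1.

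**What to change.** In Sections 2(f) and 13.2, define the participant proportion on ratings made after the first pharmacy dose: months 1, 2 and 3, plus an Early Termination rating only if it follows Visit 2. Report the Visit 1 rating separately as the OTP comparator, with a descriptive within-person change (numbers better, same and worse).

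For the smaller items, use one labelled scale in Sections 2(f), 4.4.4 and 13.2 that matches the printed form, align the visit numbers in Section 4.4.4 with Table 1, and state one start point for clinician ratings in Sections 2(g) and 4.4.4.

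The participant part costs wording only and needs no new data. The headline figure rests on 60 rather than 80 ratings for 20 completers, with the small loss of precision shown in the working. Settling the clinician start point could change when the first clinician form is due.

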3.4. Clinical and Public Health Impact

The benefits of permitting OTP physicians to prescribe methadone through community pharmacies for their stable patients are many. These include extended operating hours which improve the quality of life for working people. Delivering services closer to the patients' homes, which reduces patient burden and transportation costs. Decrease stigma associated with attending an OTP while reducing interactions between stable and unstable OTP patients. The resulting improved quality of care could reduce the likelihood of stable patients requesting premature discontinuation of treatment due to burdens associated with OTP attendance. Reduced OTP caseloads would permit admitting new patients to replace those treated in pharmacies. It will also significantly increase the professional capacity of pharmacists to provide OUD care, and most importantly, to increase the number of patients in effective treatment (Australian Institute of Health and Welfare, 2018; Chaar et al., 2011; Lawrinson et al., 2008; Matheson et al., 2007; Sheridan et al., 2007). Finally, if this model is proven feasible, acceptable, and effective, it could be expanded to treat patients with shorter periods of stability who would attend the pharmacy for more frequent dose administration.

If this pilot study is successful, the proposed service model that would permit methadone prescribing through OTPs for pharmacy dose administration and dispensing could be tested in a multi-site randomized trial, to provide data that could help to address the opioid epidemic.

4. Study Procedures/Study design

The investigative team will obtain the approvals from the Drug Enforcement Administration (DEA), Substance Abuse and Mental Health Services Administration (SAMHSA), NC State Opioid Treatment Authority (NC Department of Health and Human Services, Division of Mental Health, Developmental Disabilities and Substance Abuse Services), and Duke University Health System institutional review board (IRB) to implement this study protocol.

4.1. Participants.

A total of up to 20 OTP patients will be consented and enrolled in this study over a period of up to 12 weeks (i.e., 3 months). Given the focus on exploring the feasibility for implementation, the sample size is not powered to test for between-group efficacy or hypothesis testing.

Inclusion criteria:

1. Patient aged 18 or older receiving methadone treatment at Morse Clinic in Raleigh or Zebulon, NC.

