4.4.4. Methadone Treatment Assessments

Methadone Visit Checklist: This form will be completed by the study pharmacists to document all study medication administered and dispensed at each Pharmacy visit, including the daily prescribed dose of methadone and the lot number and expiration date of administered/dispensed medication. This form also will be used to document pharmacist-provided care, such as (1) performing methadone prescription reconciliation, (2) providing patient education (e.g., safe storage, medication side effects); (3) checking and recording the patient's controlled medications prescription status using the NC Controlled Substances Reporting System [CSRS]; (4) monitoring and recording safety related events/concerns and communicating with the OTP medical physician or staff promptly regarding the event/concern; and (5) administering one methadone dose at the pharmacy and dispensing methadone according to the prescription of the OTP physician and applicable federal/state guideline for methadone treatment for opioid use disorder. Communications between the study pharmacist and the OTP medical physician or staff will be documented on the form, such as reasons for changes in methadone doses and/or take-home schedule.

Methadone Call-Back: The OTP medical staff (e.g., nurse) will implement the call back procedure. This form will collect the written results provided from the OTP medical staff to document the outcome of each random methadone call-back visit during the study period (i.e., at least once for every study participant after the first methadone dispensing by study pharmacist(s)), including the amount of used and unused medication returned. Failure to successfully complete call back result in termination from the study and return of the participant to the OTP for further assessment and ongoing treatment. This Methadone Call-Back form will include questions assessing whether a random methadone call-back visit is completed, its date, and the outcome of the call back (e.g., brought back all doses or not). The OTP staff is required to sign and date the form that a call back was done and its results (e.g., brought back all doses or not).

Treatment Satisfaction Survey: Participants, pharmacists and methadone treatment physicians will be asked to rate their overall satisfaction with the quality of the treatment (modified from Harland et al., 2015). Participant

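### Counting satisfaction per visit gives early leavers less weight than completers and mixes in the pre-pharmacy baseline rating; call-back success has a related problem if participants have more than one call-back or leave before any

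*Combined protocol and SAP*

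**What the plan says.** **Satisfaction.** Section 13.2 calculates "The proportion of visits in which participants are satisfied" or very satisfied. Objective (f) in section 2 likewise uses the "proportion of visits in which raters are satisfied" or very satisfied. Table 1 schedules the survey at screening/baseline, at months 1, 2 and 3, and at Early Termination. Section 4.4.4 confirms the Early Termination rating for participants who discontinue and allows remote collection. Section 10 says that visit should be completed, which does not guarantee it. Under section 4.4.1, a completed missed-visit form waives all assessments due at that visit.

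**Call-backs.** Objective (b)(2) uses "the proportion of successful scheduled methadone dose call-back with no signs of methadone diversion". Section 4.4.4 adds: "Failure to successfully complete call back result in termination from the study". The Table 1 row is labelled as occurring once, while the Table 1 footnote and sections 4.4.4 and 4.5.1 require at least one. Section 13.1 words adherence as a proportion of participants and treats non-attendance at a call-back as a sign of non-adherence, so it can be read at participant level.

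**Analysis.** Section 13.3 plans descriptive analyses, with GEE to be considered for repeated outcomes. Section 13 gives no weighting, no rule for missing ratings and no denominator for people who leave. Section 4.1 says "the sample size is not powered to test for between-group efficacy or hypothesis testing".

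**The concern.** When the visit is the unit, a participant's weight is the number of ratings given. That number depends on how long the participant stayed, which may itself depend on whether the model worked for that person. Several routes out of the study suggest that it did not: a failed call-back, suspected diversion, an overdose, two consecutive missed visits, or the participant's own withdrawal.

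The baseline rating is a second difficulty. It precedes the first pharmacy visit, so it can describe only OTP care. If nobody leaves, it supplies 20 of 80 ratings, a quarter of the total.

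Acceptability is a stated aim, and the results are meant to inform a later multisite randomised trial. A reader will take the percentage as the share of people content with pharmacy dispensing, which the visit-level figure need not be. No significance test or decision threshold depends on it; what is at stake is interpretation and planning.

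**Working it through.** The plan states no expected satisfaction, drop-out or call-back failure rate, so there is no figure to reproduce. From the plan: N = 20 (the section 4.1 maximum), three follow-up ratings per completer, one Early Termination rating per leaver if obtained, and a failed call-back ending participation. Leaver numbers and all probabilities below are assumptions.

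**1. Post-transfer ratings.** Let L participants leave, each giving r post-transfer ratings. Completers are satisfied with probability c and leavers with probability q.

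- Per visit: [3(N − L)c + rLq] / [3(N − L) + rL]
- Per participant: [(N − L)c + Lq] / N
- Gap (visit minus participant): (c − q) × {L/N − rL/[3(N − L) + rL]}

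The gap is zero if c = q. It is also zero if r = 3, which is what someone leaving after month 2 and giving an exit rating contributes.

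**2. Simple case.** L = 4, leaving before month 1 with one exit rating (r = 1), c = 1, q = 0.

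- Per visit: 48/(48 + 4) = 48/52 = 92.3%
- Per participant: 16/20 = 80.0%
- With L = 2: 54/56 = 96.4% against 18/20 = 90.0%

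**3. Less extreme case.** c = 0.95, L = 4, leaving before month 1.

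- q = 0.20, per participant: (15.2 + 0.8)/20 = 80.0%. Per visit with the exit rating: (45.6 + 0.8)/52 = 89.2%, gap +9.2 points. Without it: 45.6/48 = 95.0%, gap +15.0.
- q = 0.50, per participant: (15.2 + 2)/20 = 86.0%. Per visit: (45.6 + 2)/52 = 91.5%, gap +5.5; without the exit rating 95.0%, gap +9.0.
- Over L = 2 to 6 and q = 0.20 to 0.50, the gap runs from +2.9 to +13.1 points with the exit rating and from +4.5 to +22.5 without it.

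**4. Baseline pooled in.** In the case of step 2 the ratings total 16 × 4 + 4 × 2 = 72. With baseline satisfaction b, the all-visit figure is (48 + 20b)/72.

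- b = 1: 68/72 = 94.4%
- b = 0.5: 58/72 = 80.6%
- It equals the participant figure of 80% when 48 + 20b = 57.6, that is b = 0.48, and is lower for smaller b.

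The all-visit figure can therefore err in either direction.

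**5. Call-backs.** Suppose 4 of 20 fail their first call-back and the other 16 pass all of theirs. The participant figure is 16/20 = 80.0% throughout.

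- One planned each: 16/20 = 80.0% of call-backs
- Two planned: 32/36 = 88.9%
- Three planned: 48/52 = 92.3%

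If instead everyone has the same failure risk of 10% per call-back, pooled success is 90.0% however many are planned. That is correct per call-back, but the share of participants with no failure is 0.9² = 81.0% with two planned and 0.9³ = 72.9% with three.

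People who leave before any call-back drop out of the call-back denominator even with one each. With 4 such leavers and one failure among the other 16, success is 15/16 = 93.8% of call-backs, while 15/20 = 75.0% of participants have a verified success.

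**The case against.** The strongest reply is that the plan already limits the damage. The survey is scheduled at Early Termination and may be done remotely, so leaving is not meant to end a participant's contribution. Objective (c) reports the proportion remaining at the pharmacy, so departures will be visible beside satisfaction. End-of-study interviews cover barriers. Entry requires 12 months of negative drug tests and no missed call-backs. The US experience cited in section 3.3 had no failed recalls in one report and none of 13 office-based patients leaving in the other. With a single dissatisfied early leaver the figures are 57/58 = 98.3% and 19/20 = 95%, a small difference.

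Much of this stands. Few leavers mean a small gap, and the exit rating reduces it. But one exit rating does not equal three for someone who goes before month 1, and that rating may not be obtained. Retention does not show whether leavers were dissatisfied. GEE is only to be considered, with no working correlation named, and an independence working correlation also weights by visit.

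A reader might infer that the satisfaction percentage is bound to be too favourable. The documents do not support that. It needs leavers to be less satisfied than completers, which is plausible but not shown, and some exits (pregnancy, prisoner status, lack of funding) need not reflect dissatisfaction. Pooling baseline can also move the result down.

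A reader might likewise infer that call-back success is necessarily overstated. With one call-back each, as the Table 1 label suggests, there is no over-weighting, and section 13.1 can be read as counting participants.

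**Conclusion.** The point holds in a limited form. As worded, the satisfaction percentage weights participants by the number of ratings they give and includes a rating made before any pharmacy visit, so it can misstate the acceptability of pharmacy dispensing.

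Among post-transfer ratings it is too favourable if early leavers are less satisfied. The excess is 2.9 to 13.1 points with exit ratings and 4.5 to 22.5 points without, assuming 2 to 6 of 20 leave before month 1, leavers are 20% to 50% satisfied and completers 95%. With baseline included, the direction is not determined.

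For call-backs the issue is conditional. It arises with more than one call-back per participant, or when people leave before any. The change is worth making because acceptability is a stated aim and the correction is cheap, but in a descriptive pilot no error rate or decision rule is affected.

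**What to change.** **Section 13.2.** Take as denominator all participants who received a first pharmacy dose. Report the proportion satisfied or very satisfied at their last post-transfer rating (month 3 or Early Termination). Show participants with no post-transfer rating as a separate row of the same denominator, and add a worst-case bound counting them as not satisfied. In step 3, if none of the 4 leavers gave an exit rating, that bound would be 15.2/20 = 76%. Report the baseline rating separately, as a description of OTP care. Keep the visit-level proportion, restricted to post-transfer ratings, as supporting description. Align Objective (f).

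**Section 13.1.** Over the same denominator, state the call-back result as the proportion of participants with at least one call-back and none failed, with those who had no call-back as a separate row. Align Objective (b)(2). The call-back-level percentage can stay as supporting description.

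**Cost.** A few sentences; the data are already collected, including the survey at Early Termination. The last-rating summary does not use the month 1 and month 2 ratings of those who stay, but these remain in the supporting visit-level figure.
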